6.2 DATA SHARING PLANS

6.2.1 Human Data Sharing Plan

What data will be shared?

I will share human data generated in this research for future research as follows:

x Coded and linked data in an NIH-funded or approved public repository.

x Coded and linked data in BTRIS (automatic for activities in the Clinical Center)

 \underline{x} Coded and linked or identified data with approved outside collaborators under appropriate agreements.

How and where will the data be shared?

Data will be shared through:

- x An NIH-funded or approved public repository. Insert name or names:ClinicalTrials.gov.
- x BTRIS (automatic for activities in the Clinical Center)
- _x__ Approved outside collaborators under appropriate individual agreements.
- x Publication and/or public presentations.

When will the data be shared

- x Before publication.
- \underline{x} At the time of publication or shortly thereafter.

6.3 **RESPONSE CRITERIA**

6.3.1 Disease Parameters

Measurable disease: Measurable lesions are defined as those that can be accurately measured in at least one dimension as \geq 5 mm. All measurements must be recorded in millimeters (or decimal fractions of centimeters).

Non-measurable disease. All other lesions (or sites of disease), including small lesions (longest diameter <5 mm), are considered non-measurable disease.

Target lesions. All measurable lesions will be identified as target lesions and recorded and measured at baseline.

Non-target lesions. All other lesions (or sites of disease) will be identified as non-target lesions and should also be recorded at baseline. Measurements of these lesions are not required, but the presence, absence, or in rare cases unequivocal progression of each will be noted throughout follow-up.

6.3.2 Methods for Evaluation of Measurable Disease

Lesions will be photographed, described in detail, and measured at each response evaluation. Measurements will be recorded in metric notation using a ruler or calipers. Baseline evaluations will be performed no more than 8 weeks before starting treatment.

The same method of assessment will be used to characterize each identified and reported lesion at baseline and during follow-up. Lesions will be documented by digital color photography at each response evaluation.

6.3.3 Response Criteria

6.3.3.1 Evaluation of Target Lesions

Complete Response (CR): Disappearance of all target lesions. No appearance of new lesions.

Partial Response (PR): $A \ge 50\%$ decrease in the sum of the product of the longest perpendicular diameters of target lesions, taking as reference the baseline measurements. No appearance of new lesions. No increase of greater than 25% of any index lesion.

Progressive Disease (PD): $A \ge 25\%$ increase in sum of the product of the longest perpendicular diameters of target lesions, taking as reference the smallest product on study (this includes the baseline product if that is the smallest on study). In addition to the relative increase of 25%, the sum must also demonstrate an absolute increase of at least 5 mm. (Note: the appearance of one or more new lesions is also considered progression).

Non-CR/Non-PD: Neither sufficient decrease to qualify for PR nor sufficient increase to qualify for PD, taking as reference the smallest product of diameters while on study.

Note: In the event of lesion regression with a residual abnormality of unclear significance, a biopsy may be obtained. If HSIL is present in the pathology specimen the response will be considered less than complete. If HSIL is not present the response will be considered complete.

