³ Vulvar HSIL must be HPV-16+ by PCR, RNA, or in situ hybridization test from a CLIA certified laboratory prior to treatment.

⁴ Vulvar biopsies will be performed as a punch biopsy under local anesthetic in the outpatient clinic within 8 weeks prior to starting therapy, at 2-week follow-up (day 10-14), and at 1-month follow-up (day 27-34) for all patients. An additional biopsy will be obtained at the time a patient comes off-treatment (e.g. at time of progression, at time of complete response, or at 6-month visit for patients with continuing partial response). Biopsies will be performed only if technically feasible, if they do not interfere with response assessment, and if the patient provided consent. The investigators may elect not to perform biopsies at their discretion (i.e. safety concerns, patient concerns, etc.). HSIL photographs will occur at each follow up visit. HSIL measurements will occur at baseline and at each monthly follow-up visit.

⁵ Patients' blood samples will be obtained and undergo analysis for detection of replication competent retroviruses (RCR) by PCR prior to cell infusion and at approximately 3, 6, and 12 months post cell administration. Blood samples will be archived annually thereafter if all previous testing has been negative with a brief clinical history. The ETIB preclinical core staff will cryopreserve 2 vials of cells if possible. If less than 10 million cells are available, only 1 vial of cells will be cryopreserved.

⁶ Research samples will be collected pre-treatment (within four weeks prior to cell infusion); posttreatment on post-therapy day 1, post-therapy day 3, thereafter any MWF while still an inpatient for one week, and thereafter weekly while still inpatient; and post-treatment at each research visit. For each time point, six 8mL CPT tubes will be drawn (5 for PBMC and 1 for plasma) and one 8mL SST tube (for sera). Processing and storage are as described in section **5**.

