5.1.1 Pre cell infusion evaluations

• The following samples may be drawn for research and sent to the ETIB preclinical core within 4 weeks prior to cell infusion. Send to Pre-Clinical Core lab; Attention [name], [name] contact [contact].

- 6 CPT tubes (8mL each). One CPT tube per time point may be used to collect 4mL of plasma, which may be frozen in 4mL vials. PBMC from the remainder of the CPT tubes may be frozen in aliquots of 10 x 106 cells/vial
- 1 SST tube (8mL) for sera. Serum will be processed in the ETIB Pre-Clinical Core and aliquoted into vials of 0.5-1 mL each.
- 5.1.2 Post cell infusion evaluations
 - The following samples may be drawn for research and sent to the ETIB preclinical core While the patient is inpatient, samples may be drawn on post-treatment day 1, posttreatment day 3, thereafter every Monday/Wednesday/Friday x5 days, and then weekly until discharge. Samples may also be collected at each outpatient follow-up visit. Send to Pre-Clinical Core lab; Attention [name], [name] contact [contact].
 - 6 CPT tubes (8mL each). One CPT tube per time point may be used to collect 4mL of plasma, which will be frozen in 4mL vials. PBMC from the remainder of the CPT tubes may be frozen in aliquots of 10 x 10⁶ cells/vial
 - 1 SST tube (8mL) for sera. Serum will be processed in the ETIB Pre-Clinical Core and aliquoted into vials of 0.5-1 mL each.
- 5.1.3 Optional vulvar Biopsies
 - Biopsies for research purposes will be obtained at baseline (within 8 weeks of starting treatment), 10 to 14 days after treatment, 27 to 34 days after treatment, and at the time the patient comes off-treatment (i.e. attains a complete response, experiences progression, or reaches the 6-month time point without a complete response). This biopsy schedule may be repeated for patients receiving retreatment. Clinically indicated biopsies may be obtained at any time by PI discretion if there is concern for invasive cancer.

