 - Biopsies for research will be performed with a standard punch biopsy instrument of up to 4 mm diameter. At each time point, up to 3 biopsies of HSIL lesions and up to 2 biopsies of adjacent normal tissue will be performed. A formalin-fixed paraffin embedded specimen will be transported to the NCI Laboratory of Pathology for review and archiving. The contact will be [name], [name], contact [contact]. Specimens will then be transported to the ETIB preclinical core for further processing and storage. They will be delivered to Pre-Clinical Core lab; Attention [name], [name] contact [contact].
 - Processing of biopsies will depend upon the amount of tissue obtained. Examples of processing may include OTC blocks, formalin-fixed paraffin embedding, snap freezing, placing in RNAlater or other required laboratory processing technique.
 - Biopsies will not be performed if they are not technically feasible, if they will interfere with response assessment, or if a patient declines consent.
 - Samples will be stored for this protocol. Some of these samples may be archived and analyzed under another protocol 16-C-0061 (ETIB Tissue Procurement Protocol) if the subject also coenrolled on that study.
- 5.1.4 Mandatory vulvar biopsies

- Biopsies of vulvar lesions for clinical purposes will be obtained within 8 weeks prior to starting treatment if clinically indicated to rule out invasive cancer. Biopsies will be performed in the outpatient clinic under local anesthetic.
- 5.1.4 Immunological Testing
 - Leukapheresis will be performed prior to treatment (expect for patients previously treated on protocol 17-C-0116) and 10-14 days after treatment.
 - Processing of leukapheresis will be in the Department of Transfusion Medicine (DTM). Cell product may be frozen in 10 vials at concentration 100 x 10⁶ cells/mL and additional vials at 300 x 10⁶ cells/mL. Cells will be stored in a -80 degrees Celsius freezer in DTM overnight and transferred to the ETIB Preclinical Core the following day. Samples will be sent to Pre-Clinical Core lab; Attention [name], [name]. Contact [contact].
 - At other time points, peripheral blood lymphocytes (PBL) and plasma may be obtained from whole blood by purification using centrifugation. These samples will be transferred directly to the ETIB Pre-Clinical Core lab for processing. Plasma may be frozen in 4mL vials. PBL may be frozen in aliquots of 10 x 10⁶ cells/vial.

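### Does the plan need a rule for HSIL found in the optional biopsy taken at complete response?

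*Combined protocol and SAP*

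**What the plan says.** Section 6.3.3.1 defines target-lesion CR by clinical inspection: every target lesion gone and no new ones. The table in 6.3.3.3 builds overall response from target, non-target and new-lesion status and has no histology column. Section 6.3.4 dates a CR from when the measurements first qualify.

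Histology enters in one place, the Note closing 6.3.3.1: "In the event of lesion regression with a residual abnormality of unclear significance, a biopsy may be obtained". Two outcomes follow: "If HSIL is present in the pathology specimen the response will be considered less than complete", and "If HSIL is not present the response will be considered complete".

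A biopsy is also scheduled at CR. Footnote 4 of the study calendar (3.3) states: "An additional biopsy will be obtained at the time a patient comes off-treatment (e.g. at time of progression, at time of complete response". The same footnote adds a condition: "Biopsies will be performed only if technically feasible, if they do not interfere with response assessment, and if the patient provided consent". Section 5.1.3, headed as optional biopsies and describing them as taken for research, repeats the timing: "at the time the patient comes off-treatment (i.e. attains a complete response, experiences progression". At each time point "up to 3 biopsies of HSIL lesions and up to 2 biopsies of adjacent normal tissue will be performed", and "A formalin-fixed paraffin embedded specimen will be transported to the NCI Laboratory of Pathology for review and archiving".

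Section 10.1.3 sets the decision rule: stop if none of 12 patients has a CR, otherwise go to 16, with 3 or more CRs counted as worth further study. The null and target CR rates are 5% and 25%.

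**The concern.** A pathology result will exist for some patients already scored as clinical CR, and nothing says what HSIL in it would do to the score. Read literally, the plan is lopsided. A negative biopsy can turn a visible residual into a CR, but a positive biopsy taken at CR removes nothing. Section 5.1.3 also does not say which site is sampled once no lesion is left, and 10.1.3 does not say whether 5% and 25% are clinical or biopsy-checked rates.

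The margins are thin. Three CRs in 16 (18.75%) is success and two (12.5%) is not; one in 12 opens stage 2 and none stops the trial. If the rule were picked after the pathology was known, that choice could settle the result.

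**Working it through.** **Inputs.** From 10.1.3: 12 patients then 16, stop at 0/12, success at 3/16 or more, p0 = 0.05, p1 = 0.25, alpha 0.10, beta 0.20, early termination 54.0% under p0. The share f of clinical CRs that contain HSIL is not in the documents; 10%, 20% and 33% (one third) are assumed values.

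**1. The plan's own figures.** At CR probability p,

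P(success) = P(Bin(16, p) ≥ 3) − (1 − p)^12 × P(Bin(4, p) ≥ 3),

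where the second term removes trials stopped at 0/12.

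- p = 0.05: early termination is 0.95^12 = 0.5404, matching 54.0%. P(success) = 0.04294 − 0.5404 × 0.00048 = 0.0427.
- p = 0.25: P(success) = 0.80289 − 0.0317 × 0.0508 = 0.8013.

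The design meets both limits, with room on alpha and almost none on power.

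**2. Plain reading.** Section 10.1.3 uses the term that 6.3.3 defines. If 5% and 25% are rates of that CR, the scheduled biopsy does not enter the count, and 0.0427 and 0.8013 apply unchanged.

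**3. Histologic reading.** Suppose instead that 5% is the true clearance rate and every clinical CR is still counted. The clinical rate is then q = 0.05/(1 − f).

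| f (assumed) | q | P(success) | Excess over 0.0427 | Early stopping (1 − q)^12 | Fall from 0.5404 |
|---|---|---|---|---|---|
| 10% | 0.0556 | 0.0555 | 0.0128 | 0.5036 | 0.037 |
| 20% | 0.0625 | 0.0738 | 0.0311 | 0.4610 | 0.079 |
| 33% | 0.0750 | 0.1129 | 0.0702 | 0.3924 | 0.148 |

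The excess is the chance that success rests on HSIL-positive CRs. The last column is the chance that stage 2 opens only because of them. P(success) reaches 0.10 at q = 0.0711, so f = 1 − 0.05/0.0711 = 0.297.

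If exactly three CRs are seen, the chance that at least one contains HSIL is 1 − (1 − f)^3 = 27%, 49% or 70%. This restates the assumption and is not evidence for it.

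**4. What downgrading would do.** If 25% is the clinical rate and every CR is biopsied, the counted rate is 0.25(1 − f):

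- f = 10%: 0.225, power 0.731
- f = 20%: 0.200, power 0.646

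If only half of CRs are biopsied (assumed), the counted rate is 0.25(1 − 0.5f) and power is 0.768 or 0.731. All four values miss the planned 0.80.

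On the histologic reading of step 3, with half biopsied, the counted rate is q(1 − 0.5f) = 0.0528, 0.0563 or 0.0625. P(success) is then 0.049, 0.057 or 0.074, against 0.055, 0.074 or 0.113 with no downgrading. Partial biopsy therefore removes only part of the excess.

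**The case for a change.** The strongest case for a change does not rest on any error rate. A primary endpoint should have one reading, fixed in advance. The Note shows that the authors regard pathology as decisive when there is doubt, and eligibility under 2.1.1.4 requires histology for recurrent disease. A reader could extend the Note's principle to the biopsy at CR. The wording on best recorded response in 6.3.3.3 could equally let the CR stand. The trial is single-arm, the principal investigator reviews the response data (7.5.1), and no independent response review is described.

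It is true that no sentence addresses this specimen. But the two readings are not equally supported. CR is defined, tabulated and dated without it. The specimen is optional and taken for research, and footnote 4 rules out biopsies that would interfere with response assessment. The Note already covers the doubtful case, a residual area that someone chooses to biopsy. What is left is tissue with nothing visible in it, and the limit on HSIL samples in 5.1.3 allows none when no lesion remains. The documents do not show that such specimens would be common.

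Histologic downgrading would also bring its own asymmetry. A patient who consents to biopsy could lose her CR, while an identical patient who declines would keep it.

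**Conclusion.** No change is needed. Following the plan as written gives a valid count of clinical CRs, with type I error 0.043 and power 0.801. The missing sentence is a gap that an analyst fills sensibly: the clinical CR stands, and any biopsy results at CR are described beside the count as HSIL-negative, HSIL-positive or not biopsied.

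An inflated error rate needs two things that the documents do not supply: a histologic meaning for 5% and a share of false CRs. With both granted, the stated 0.10 is passed only when about 30% or more of clinical CRs contain HSIL. Letting the optional biopsy overrule the clinical call is a trade-off, not a correction. It ties the primary endpoint to consent and feasibility and, if 25% is a clinical rate, takes power below 80% at every assumed share examined. Spelling out in 10.1.3 which CR is meant would only record the plain reading.

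This conclusion rests on 10.1.3 using CR in the sense of 6.3.3. It would weaken if the 5% and 25% rates had been drawn from biopsy-confirmed responses, which the text does not indicate.

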6.3.3.2 Evaluation of Non-Target Lesions

Complete Response (CR): Disappearance of non-target lesions.

Progressive Disease (PD): Appearance of one or more new lesions and/or unequivocal progression of existing non-target lesions. It must be representative of the overall non-target disease rather than an increase in a single lesion.

Non-CR/Non-PD: Persistence of one or more non-target lesion(s).

6.3.3.3 Evaluation of Best Overall Response

The best overall response is the best response recorded from the start of the treatment until disease progression/recurrence (taking as reference for progressive disease the smallest measurements recorded since the treatment started).

For Patients with Measurable Disease (i.e., Target Disease)

	Target Lesions	Non-Target Lesions	New Lesions	Overall Response
--	-------------------	-----------------------	----------------	------------------

CR	CR	No	CR		
CR	Non- CR/Non-PD	No	PR		
CR	Not evaluated	No	PR		
PR	Non- CR/Non- PD/not evaluated	No	PR		
Non- CR/Non- PD	Non- CR/Non- PD/not evaluated	No	Non-CR/Non-PD		
PD	Any	Yes or No	PD		
Any	PD*	Yes or No	PD		
Any	Any	Yes	PD		
 In exceptional circumstances, unequivocal progression in non-target lesions may be accepted as disease progression. Note: Patients with a global deterioration of health status requiring discontinuation of treatment without objective evidence of disease progression at that time should be reported as "symptomatic deterioration." Every effort should be made to document the objective progression even after discontinuation of treatment. 					

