⁷ All patients will follow-up at 1, 2, and 3 months after cell infusion (+/- 7 days). Patients with no response at the 3-month evaluation will be referred for standard of care therapy. Patients with a partial or complete response at the 3-month evaluation will continue to follow up at 4, 5, and 6 months for safety, response, and research evaluations (+/- 7 days). After the 6-month response assessment patients with partial response will be referred for standard of care therapy and patients with a complete response will continue to have follow-up every 3 months (+/- 30 days) for 2 visits, then every 6 months (+/- 30 days) for 2 visits (2 years of follow up total). ⁸As indicated in section 10.4, all subjects \geq age 18 will be offered the opportunity to complete an NIH advanced directives form. This should be done preferably at baseline but can be done at any time during the study as long as the capacity to do so is retained. The completion of the form is strongly recommended, but is not required.

⁹Subjects or local treating physician will be contacted to collect information annually for five years after the date of cell infusion:1) procedures or treatments for vulvar HSIL, 2) procedures or treatments for cervical, vaginal, or anal intraepithelial neoplasia, 3) occurrence of vulvar, cervical, or anal cancer. This followup can be conducted via telephone.

¹⁰Clinical assay may be performed at these time points by the NCI Flow Cytometry Laboratory in the Laboratory of Pathology.

¹¹If applicable, see section 2.1.2.6.

¹²Except for patients previously treated on protocol 17-C-0116.

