3.6.1 Criteria for removal from protocol therapy

Note: Subjects removed from protocol therapy may still be eligible for up to one course of retreatment per section **3.4**. The same off treatment criteria apply after the second potential course as for the first. Data collection and assessments required while off therapy are addressed in sections **6.1** and **3.3** respectively.

- Completion of protocol therapy
- Positive pregnancy test
- Progression of disease
- Participant requests to be withdrawn from active therapy
- Investigator discretion
- Unacceptable toxicity

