6 DATA COLLECTION AND EVALUATION

6.1 DATA COLLECTION

The PI will be responsible for overseeing entry of data into an in-house password protected electronic system (C3D) and ensuring data accuracy, consistency and timeliness. The principal investigator, associate investigators/research nurses and/or a contracted data manager will assist with the data management efforts. All data obtained during the conduct of the protocol will be kept in secure network drives or in approved alternative sites that comply with NIH security standards. Primary and final analyzed data will have identifiers so that research data can be attributed to an individual human subject participant.

All adverse events, including clinically significant abnormal findings on laboratory evaluations, regardless of severity, will be followed until return to baseline or stabilization of event.

Document AEs from the first study intervention, Study Day 0 through 28 days after removal from the study treatment, or until off-study, or until they initiate a new treatment, whichever comes first. Beyond 28 days after the last intervention, or initiation of new treatment as applicable, only adverse events and serious adverse events that are at least possibly related to E7 TCR T cells will be recorded. Grade 1 adverse events will not be recorded.

An abnormal laboratory value will be recorded in the database as an AE **only** if the laboratory abnormality is characterized by any of the following:

- Results in discontinuation from the study
- Is associated with clinical signs or symptoms
- Requires treatment or any other therapeutic intervention
- Is associated with death or another serious adverse event, including hospitalization.
- Is judged by the Investigator to be of significant clinical impact
- If any abnormal laboratory result is considered clinically significant, the investigator will provide details about the action taken with respect to the test drug and about the patient's outcome.

End of study procedures: Data will be stored according to HHS, FDA regulations and NIH Intramural Records Retention Schedule as applicable.

Loss or destruction of data: Should we become aware that a major breach in our plan to protect subject confidentiality and trial data has occurred, this will be reported expeditiously per requirements in section 7.2.1.

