10.1.3 Sample Size Determination

This trial will be conducted using a Simon minimax two-stage phase II trial design(25) to rule out an unacceptably low CR rate of 5% (p0=0.05) in favor of an improved complete response rate of 25% (p1=0.25). With alpha=0.10 (probability of accepting a poor treatment=0.10) and beta = 0.20 (probability of rejecting a good treatment=0.20), the first stage will enroll 12 evaluable patients, and if 0 of the 12 have a complete response, then no further patients will be accrued. If 1 or more of the first 12 patients have a complete response, then accrual would continue until a total of 16 evaluable patients have been treated. As it may take up to several months to determine if a patient has experienced a complete response, a temporary pause in the accrual may be necessary to ensure that enrollment to the second stage is warranted. If there are 1-2 patients with a complete response out of 16 patients, this would be an uninterestingly low

complete response rate. If there were 3 or more of 16 (18.75%) who experienced a complete response, this would be sufficiently interesting to warrant further study in later trials. Under the null hypothesis (5% complete response rate), the probability of early termination is 54.0%. In patients that undergo retreatment, only the first response to E7 TCR T cell treatment will be used in the calculation of complete response rate.

Since patients will be screened on this protocol, to allow for patients who enroll but are not evaluable for the primary endpoint, as well as screen failures, up to 200 patients total may be enrolled. It is expected that up to 10-12 treated patients can be enrolled within one year; thus, up to 18 months may be required to accrue 16 evaluable patients. Up to 16 patients may be treated in order to allow for a small number of inevaluable, treated patients.

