10.1.4 Populations for Analyses

Toxicity Analysis: All patients will be evaluable for toxicity from the time of E7 TCR T cell infusion. Toxicity data will be collected for all patients.

Response Analysis - Intention to treat: any subjects who enroll onto the trial and provide consent and who receive at least one cycle of treatment will be included in analyses.

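### Does the missing scoring rule for other vulvar HSIL treatment started before the last response evaluation leave the complete response rate open to choice?

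*Combined protocol and SAP*

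**What the plan says.** **Response window.** Section 6.3.3.3: "The best overall response is the best response recorded from the start of the treatment until disease progression/recurrence". Section 6.3.3.1 defines CR by the disappearance of target lesions with no new ones, without reference to cause. Neither section mentions other treatment for the vulvar lesions.

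**Schedule.** Section 3.3, footnote 7: "All patients will follow-up at 1, 2, and 3 months after cell infusion". Non-responders are referred to standard care after month 3. Partial and complete responders are seen again at months 4, 5 and 6, and partial responders are referred after the month 6 assessment. Response evaluation appears only in the monthly follow-up column.

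**Early removal.** Section 3.6.1 lists, among other reasons, "Participant requests to be withdrawn from active therapy", and points to sections 6.1 and 3.3 for what is collected afterwards.

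**Adverse events.** Section 6.1 runs full documentation to the earliest of several dates, including "or until they initiate a new treatment, whichever comes first". After that, events at least possibly related to the cells are still recorded.

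**Endpoint and population.** Sections 1.1.1 and 10.1.1 define the endpoint as the CR rate for the E7 TCR T cells. Section 10.1.4 says of the response population: "any subjects who enroll onto the trial and provide consent and who receive at least one cycle of treatment will be included in analyses". Section 10.1.3 states the decision rules in terms of evaluable patients and adds: "Up to 16 patients may be treated in order to allow for a small number of inevaluable, treated patients".

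**The concern.** The safety section foresees a new treatment and changes what is recorded from that date; the efficacy section has no counterpart. A patient could leave protocol follow-up early in all but name, have her lesions excised or treated topically at week 10, and be free of lesions at the month 3 visit. On the literal wording of sections 6.3.3.1 and 6.3.3.3 she has a CR. On section 10.1.4 she is a treated patient whom the cells did not clear. On section 10.1.3 someone might call her inevaluable.

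The trial is small, single-arm and decided by counts: one CR in the first 12 opens stage 2, and three in 16 make the treatment worth pursuing. A choice about one patient, made after her outcome is known, could decide either step, and no control arm would reveal the error.

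**Working it through.** **Inputs** (section 10.1.3): p0 = 0.05, p1 = 0.25, alpha 0.10, beta 0.20; stop if 0 of 12 have a CR; positive if at least 3 of 16 do.

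**1. The plan's own figures.**
- Early termination at p0: 0.95^12 = 0.540, as stated.
- P(positive) = P(X ≥ 3 of 16) − P(0 of 12) × P(X ≥ 3 of 4).
- At 5%: 0.0429 − 0.5404 × 0.00048 = 0.0427.
- At 25%: 0.8029 − 0.0317 × 0.0508 = 0.8013.

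The design reproduces and meets its limits.

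**2. One affected stage 1 patient, credited with a CR.** Stage 2 opens automatically, and 2 more CRs are needed among the other 15.
- At 5%: 1 − 0.95^15 − 15 × 0.05 × 0.95^14 = 1 − 0.4633 − 0.3658 = 0.171.
- At 25%: 0.920.

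**3. The same patient, scored non-CR.** At least 1 CR is needed among the other 11 in stage 1, and at least 3 among the other 15 overall.
- At 5%: P(X ≥ 3 of 15) − 0.95^11 × P(X ≥ 3 of 4) = 0.0362 − 0.5688 × 0.00048 = 0.0359.
- At 25%: 0.762.

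**4. The same patient, dropped as inevaluable.** Section 10.1.3 caps treated patients at 16, so 15 remain. With the threshold left at 3 and stage 1 filled to 12 evaluable patients, P(positive) is 0.0361 at 5% and 0.7634 at 25%. This is practically the non-CR result. Only the reported fraction differs, for example 3/15 = 20% against 3/16 = 18.75%. The scoring that matters is CR against not CR.

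**5. Less than certain clearance.** Step 2 assumes that she is certain to be cleared of all lesions and credited. If she is cleared and credited with probability c, P(positive) at 5% is 0.0359 + c × (0.1710 − 0.0359):
- c = 0.25: 0.070
- c = 0.50: 0.103

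These values of c are assumptions.

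**6. Break-even.** P(positive) reaches 0.10 at an apparent CR rate of 0.0711. The share of patients without a CR who would have to be cleared by other treatment inside the window, and counted, is (0.0711 − 0.05)/0.95 = 0.022, about 1 in 45. The documents give no rate to compare with this.

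**7. Who is exposed.** By footnote 7, only a patient without a CR who starts other treatment before month 3, or a partial responder who does so between months 3 and 6. A CR recorded earlier stands. Planned referral falls after the last scoring in both groups.

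**The case for a change.** The best case for a change is that the text really is silent. No sentence in sections 3.6, 6.3 or 10 says that evaluations after other treatment do not count. The situation can arise: section 3.6.1 allows early removal, section 4.1 restricts only systemic steroids, and section 1.2.2 names topical imiquimod as an alternative for some patients. Two sentences would settle the matter before data are seen.

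The silence stands. Several supports for the argument do not:

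- The contrast with section 6.1 is weaker than it looks. Adverse event recording is narrowed at a new treatment, not ended, and response scoring need not share its cut-off.
- The request in section 6.3.3.3, "Every effort should be made to document the objective progression even after discontinuation of treatment", concerns patients with symptomatic deterioration. It does not ask for responses to be scored after other treatment.
- Evaluable against all-treated patients is a general question about the denominator, present with or without other treatment.
- Early full clearance by other means is not the expected course. Section 2.1.1.3 admits patients for whom surgery has failed or would have results they do not accept, and section 1.2.2 says inflammation and pain limit imiquimod.
- The information would not be hidden. History, examination and concomitant medications are due at every monthly visit, with photographs and lesion measurements, although there is no dedicated field for an HSIL procedure.

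One textual caution: the sentence in section 10.1.3 that counts only the first response to the cell treatment is written for retreated patients. It shows that the response meant is a response to the cells, but it is not a rule for this case.

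**Conclusion.** No change is needed. This is an unwritten detail for an uncommon case, and the plan's text points to one sensible answer. The endpoint is a response to the T cells, and all treated patients are analysed. Clearance that follows surgery or topical treatment is therefore not counted, and the patient stays in the denominator as a non-CR unless a CR was recorded before the other treatment began.

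That scoring errs on the cautious side. With one affected stage 1 patient, the false-positive probability is 0.036, below the design's 0.043, and power is 76.2% instead of 80.1%. The figure of 0.171 arises only if clearance is certain and an analyst credits it to the cells against the stated endpoint. The sample size, both decision rules and the 54.0% early termination figure are unaffected.

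The conclusion rests on two assumptions: that such treatment before month 3 (or month 6 in partial responders) is rare, which the documents suggest but do not quantify, and that the analyst reads CR as a response to the study treatment.
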